5.2 Model-based Dose Escalation Rules

The initial dose-escalation portion of the trial will be conducted using the modified toxicity probability interval (mTPI) method ([Ji 2010](#)). This part of the study is designed to evaluate the safety and tolerability, and to identify the MTD of SEA-BCMA. The mTPI design uses a Bayesian statistical framework and a beta/binomial hierachic model to compute the posterior

probabilities of 3 intervals that reflect the relative distance between the toxicity rate of each dose level to the target DLT rate. Using a target DLT rate of 25% with a 5% margin, the 3 intervals will be (0, 20%), [20%, 30%] and (30%, 100%), and the corresponding dosing decision rules would be:

1. Escalate if current DLT rate is most likely < 20%
2. Continue if current DLT rate is most likely between 20% and 30%
3. De-escalate if current DLT rate is most likely > 30%

Dose finding decisions are shown in [Table 2](#). E, S, and D represent escalating the dose, staying at the same dose, and de-escalating the dose, respectively. Decision DU means that the current dose level has an unacceptably high toxicity rate and should be excluded from the trial.

Enrollment in this study will occur on a cohort-by-cohort basis. Multiple cohorts may be treated at each dose level, with a maximum of 4 patients treated per cohort. Decisions on dose escalation and subsequent cohort size will be made by the sponsor in consultation with the safety monitoring committee (SMC) after completion of each cohort. Patients in the current cohort must be observed for the full duration of the DLT period before the next cohort of patients is enrolled. In addition, as a precaution, for the first 2 patients in the study there will be a 72-hour observation period before the next patient can be dosed. At doses above Dose Level 1, a 72-hour observation period is required after the first patient in each cohort receives their first dose of SEA-BCMA prior to dosing subsequent patients in the cohort. At least 2 DLT-evaluable (DE) patients will be treated per dose level until the first DLT is observed, then a minimum of 3 DE patients per dose level will be required before escalation to all higher doses. Patients who are considered not evaluable for DLT during Cycle 1 may be replaced. A minimum of 6 DE patients will be observed at the estimated MTD before the MTD or optimal dose is determined. The MTD or optimal dose will be estimated based on data from all patients across all evaluated doses.

De-escalation to a lower dose level may be performed at any time by the sponsor in consultation with the SMC. Intrapatient dose escalation to a dose level shown to be safe may be permitted in the event that a patient tolerates SEA-BCMA and achieves stable disease (SD) or better.

Patients may continue on treatment until progressive disease or unacceptable toxicity, whichever occurs first.

Table 2: Dose-finding spreadsheet for mTPI design

Number of DLTs	Number of DLT-evaluable patients treated at current dose														
	2	3	4	5	6	7	8	9	10	11	12	13	14	15	
0	E	E	E	E	E	E	E	E	E	E	E	E	E	E	E
1	S	S	S	S	E	E	E	E	E	E	E	E	E	E	E
2	DU	D	D	S	S	S	S	S	S	S	S	S	E	E	
3	DU	DU	DU	D	S	S	S	S	S	S	S	S	S	S	
4		DU	DU	DU	DU	D	S	S	S	S	S	S	S	S	
5			DU	DU	DU	DU	DU	DU	D	S	S	S	S	S	
6				DU	D	S									
7					DU										
8						DU									
9							DU								
10								DU							
11									DU	DU	DU	DU	DU	DU	
12										DU	DU	DU	DU	DU	
13											DU	DU	DU	DU	
14											DU	DU			
15												DU			

E = escalate to the next higher dose, S = stay at the current dose, D = de-escalate to the next lower dose, DU = current dose is unacceptably toxic

At the end of the trial when the toxicity outcomes of all the enrolled patients are observed, a dose will be selected as the estimated MTD. The estimation is separated from the design for dose finding. The MTD is selected by performing an isotonic regression that borrows strength cross doses. Let \hat{p}_i be the posterior mean of DLT rate, the pooled adjacent violators algorithm (PAVA) is applied on \hat{p}_i^* so that the resulting transformed values \hat{p}_i^* increase with the dose levels. That is $\hat{p}_i^* \leq \hat{p}_{i+1}^*$ for all i . The recommended MTD is the dose with a toxicity probability \hat{p}_i^* closest to the target DLT rate 25%, i.e.:

$$\text{Estimated MTD} = \text{argmin} |\hat{p}_i^* - 25\%|.$$

5.3 Determination of Sample Size

Up to approximately 131 subjects are expected to be enrolled in this study. This number is based on the following assumptions:

- Up to approximately 45 subjects will be evaluated in Part A (monotherapy dose-escalation and expansion; q2wk dosing).

With the mTPI study design, the exact number of subjects needed to complete the dose-escalation portion of the phase 1 study is unknown because it depends on the number of cohorts required to reach MTD and the number of subjects enrolled in each cohort. This number is based on the assumption that approximately 25 subjects will be evaluated in dose-escalation and that approximately 20 subjects will be evaluated in an expansion cohort at the MTD or optimal dose to further define the safety and antitumor activity of SEA-BCMA.

Operating characteristics of the dose-escalation part of the study, including the average number of subjects allocated to each dose across a variety of toxicity scenarios are presented in the simulation report which is in appendix of protocol.

- Up to approximately 20 subjects will be evaluated in Part B, up to 60 subjects will be evaluated in Part C (up to 20 subjects in Cohort 1; up to 20 subjects in each dose level in Cohort 2) and up to 6 subjects will be evaluated in Part D.

No formal hypothesis is planned. The sample size is selected by providing a reasonable estimation precision. Assuming the observed ORR is between 30 to 70%, the 95% binomial exact CIs are summarized below.

ORR	95% CI (N=20)
30%	12%, 54%
40%	19%, 64%
50%	27%, 73%
60%	36%, 81%
70%	46%, 88%

5.4 Randomization and Blinding

This is a single-arm, open-label study. No randomization or blinding will be utilized.

5.5 Data Transformations and Derivations

Reported age in years will be used; if not available, age in years will be calculated with the SAS INTCK function (with method specified as “continuous”) using informed consent date and birth date.

Study Day will be calculated as Date – First Dose Date + 1 for dates on or after the first dose date. For dates prior to the first dose date, Study Day will be calculated as Date – First Dose Date. For all calculations of Study Day, the First Dose Date will be the earliest date of treatment administration for SEA-BCMA.

Other time variables based on two dates, e.g., Start Date and End Date, will be calculated as (End Date – Start Date + 1) (in days) unless otherwise specified in the planned analysis section.

The following unit conversion will be implemented unless otherwise specified:

$$\text{Months} = \text{Days} / 30.4375$$

$$\text{Years} = \text{Days} / 365.25$$

Unless otherwise specified, baseline values used in all analyses will be the most recent non-missing measurement prior to the first dose of study drug.

The end-of-treatment (EOT) date will be the date the EOT visit is performed; if an EOT visit is not performed then the EOT date will be either the (end-of-study) EOS date or 30 days after the last dose of any study drug, whichever is earlier.

For efficacy assessments, the date of response will be the latest of all disease evaluations for the given restage assessment. The date of progression will be the earliest of all disease evaluations for the given restage assessment, or the date of investigator claim of clinical progression. Patients who have a response of stable disease or better per IMWG uniform response criteria at the same visit as investigator claim of clinical progression will be counted as clinical progression for determination of best clinical response. An investigator claim of clinical progression is adequate for an assessment of disease progression. For subjects who had C1D22 confirmed response of SD while unconfirmed response as PD and then discontinued treatment without receiving any additional treatment after cycle 1, the best confirmed response will be counted as PD.

5.6 Handling of Dropouts and Missing Data

With the exception of the scenarios covered in this section, missing data will not be imputed.

AE dates will be imputed for the purpose of calculating duration of events and treatment-emergent status (see [Appendix A](#) for imputation details). Censoring will be described in Section 6 with each planned analysis, as applicable.

Unless otherwise specified, lab values which are recorded or provided as being less than the lower limit of quantification (LLOQ), will be included in figures and summaries as LLOQ. For the purpose of grading, lab values reported as less than LLOQ will be imputed as LLOQ.

5.7 Multicenter Studies

There are multiple centers in this study, however it is not anticipated that any center will accrue enough patients to warrant an analysis by center.

5.8 Multiple Comparison/Multiplicity

No multiple comparisons are planned and no alpha adjustment is needed in this phase 1 study.

5.9 Examination of Subgroups

As exploratory analyses, subgroup analyses may be conducted for selected endpoints. Subgroups may include but are not limited to the following:

- Age (<65 vs \geq 65 years old)
- BCMA expression levels

5.10 Covariates

This is a phase 1 study. Covariates are not considered for adjustment in the analyses.

5.11 Timing of Analyses

The final analysis for this study will occur after all subjects have completed their treatment and the follow-up period or following study termination by the sponsor.

6 PLANNED ANALYSES

6.1 Disposition

An accounting of study patients by disposition will be tabulated by dose level and total using the All Treated Patients analysis set. Reasons for discontinuation of treatment and study will be summarized.

6.2 Demographic and Baseline Characteristics

Demographics and baseline characteristics, including age, gender, ethnicity, race, baseline height, weight, and ECOG score will be listed and summarized; summaries will be presented for each dose level and total using the All Treated Patients analysis set. Disease specific characteristics, including the following measurements at initial diagnosis: M protein, light chain type, ISS stage, chromosomal abnormalities, LDH; refractory or intolerant to selected classes of therapy (PI, IMiD, Anti-CD38 antibody); time from diagnosis; and previous cancer-related treatments will be listed and summarized for each dose level and the total using the All Treated Patients analysis set.

6.3 Protocol Deviations

Important protocol deviations (defined as protocol violations by Seattle Genetics) are those that represent a divergence from the protocol that could have a significant effect on the integrity of the study data, or on the subject's rights, safety, or welfare. Important protocol deviations also include exemptions to the study inclusion/exclusion criteria and will be summarized by category. A list of patients with important protocol deviations will be presented.

6.4 Treatment Administration

Treatment administration will be summarized by dose level using the All Treated Patients analysis set. Summary statistics for duration of therapy and the number of cycles per patient will be presented, as well as the number and percentage of patients who were treated at each cycle. Cumulative dose, absolute dose intensity (ADI) and relative dose intensity (RDI) will be described. The number and percentage of patients whose dose was ever modified will be summarized in tables by modification type, cycle, and overall (i.e. over all drug administrations for a patient); listings may be presented as well.

Duration of treatment (except when calculating exposure) is defined as the time from first dose date to the earliest of :

1. Last cycle day 1 dose date + length of one dosing cycle (i.e., 28),
2. date of death

3. End of study date
4. Analysis data cutoff date if the subject is still on treatment at the time of data cutoff for an analysis.

For the purpose of calculating exposure summaries, duration of treatment is defined as below:

For q2wk schedule: $[(\text{last dose date} + 14) - \text{first dose date}]$.

For the schedule of q1wk induction for 8 weeks (2 cycles), followed by q2wk dosing:

- If subjects received 2 or less cycles, $[(\text{last dose date} + 7) - \text{first dose date}]$.
- If subjects received 2 and more cycles, $[(\text{last dose date} + 14) - \text{first dose date}]$.

Intended Dose Intensity (IDI) is defined as the intended dose of drug (mg) per unit of time. For an initial dose of 100 mg, this is $100 \text{ mg} / 2 \text{ weeks} = 50 \text{ mg/wk}$ with q2wk schedule.

For the schedule of q1wk induction for 8 weeks (2 cycles), followed by q2wk dosing, the IDI is as below.

Initial dose ^a	Total cycles (nc)	Intended total number of doses(nd)	IDI
1600 mg	≤ 2	$4 * \text{nc}$	1600 mg/wk
1600 mg	> 2	$4 * 2 + (\text{nc} - 2) * 2$ $= 2 * \text{nc} + 4$	$(1600 * \text{nd}) / (4 * \text{nc})$ mg/wk

^a: the algorithm is similar for other initial dose level.

Absolute Dose Intensity (ADI) is defined as the actual dose (mg) per unit of time that the patient received over the entire treatment period.

Relative dose intensity (RDI) is defined as the absolute dose intensity over the intended dose intensity.

$$\text{RDI} = \text{ADI} / \text{IDI} * 100\%$$

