3.1.2. Part B: Monotherapy Intensive Dosing

Part B will evaluate the safety and tolerability of SEA-BCMA dosed q1wk during an induction phase (for 8 doses during the first 2 cycles of therapy); following the completion of the 8 week induction phase, subjects who have not yet experienced confirmed disease progression may proceed to receive SEA-BCMA dosed q2wk during a maintenance phase (Cycle 3 and beyond, dosing at the recommended standard-schedule monotherapy expansion dose determined in Part A).

Part B will include a safety run-in at the recommended SEA-BCMA monotherapy expansion dose (1600 mg), administered on the intensive dosing schedule (Day 1, Day 8, Day 15, and Day 22 of Cycles 1 and 2, and Day 1 and Day 15 of subsequent cycles). DLTs will be evaluated in the first 6 subjects.

4. If 0 or 1 of the first 6 subjects experience DLT, the expansion cohort will proceed to enroll up to 20 total subjects with the recommendation of the SMC.
5. If ≥ 2 DLTs occur in the first 6 subjects, MTD will be considered exceeded and the dose of SEA-BCMA will be de-escalated to the next lower dose level (800 mg q1wk x 8 weeks during Cycles 1 and 2, followed by 1600 mg q2wk from Cycle 3 and beyond).
 - If 0 or 1 of the first 6 subjects at the lower dose level experience a DLT, the expansion cohort will proceed to enroll up to 20 total subjects at this dose level with the recommendation of the SMC.
 - If ≥ 2 DLTs occur in the first 6 subjects at the lower dose level, MTD will be considered exceeded, and the Part B Monotherapy Intensive Dosing cohort will be discontinued.

Subjects who are deemed not evaluable for DLT during dose finding will be replaced.

Table 4: Planned dose levels for Part B

Dose Level	Weekly Induction Dose, Cycles 1-2 (mg)	Biweekly Maintenance Dose, Cycles 3 and beyond (mg)
1	1600	1600
-1 (if Dose Level 1 is not tolerated)	800	1600

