3.1.4. Duration of Treatment

Subjects in all cohorts may continue on treatment until disease progression, unacceptable toxicity, withdrawal of consent, death, or study termination, whichever occurs first.

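### On the intensive schedule, SAP 6.4 gives two exposure times at exactly two cycles and, beyond two cycles, sets whole-cycle intended dose against actual time, so a fully compliant subject need not have an RDI of 100%

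*SAP*

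**What the plan says.** SAP Section 6.4 defines a separate treatment duration for exposure summaries. For the schedule of weekly induction over two cycles followed by dosing every two weeks, it has two bullets. The first, "If subjects received 2 or less cycles", runs exposure from first dose to last dose plus 7 days. The second, "If subjects received 2 and more cycles", runs it to last dose plus 14 days.

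The table of intended dose intensity (IDI) in the same section splits differently, at two or fewer cycles and more than two. In the first band IDI at 1600 mg is 1600 mg/wk. In the second, with nc cycles, the intended number of doses is 2nc + 4, spread over 4nc weeks.

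Absolute dose intensity (ADI) is "the actual dose (mg) per unit of time that the patient received over the entire treatment period". The ratio is then stated: "Relative dose intensity (RDI) is defined as the absolute dose intensity over the intended dose intensity".

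The section also has a general treatment duration that adds a full cycle to the last Day 1 dose, but expressly sets it aside for exposure calculations. It does not say whether a cycle that was started but not finished counts toward nc.

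**The concern.** There are two separate faults.

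First, the duration bullets overlap. Someone with exactly two cycles can be given either end date, and RDI changes with the choice. This is a likely place to stop: under Protocol Section 3.1.2 the switch from induction to maintenance comes after Cycle 2, and only subjects without confirmed progression may go on.

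Second, beyond two cycles numerator and denominator use different clocks. IDI counts whole cycles, while ADI stops 14 days after the last dose. Stopping partway through a cycle is normal in this trial: "Subjects in all cohorts may continue on treatment until disease progression, unacceptable toxicity, withdrawal of consent, death, or study termination, whichever occurs first". With the counting of a partial cycle left open, RDI can differ from 100% with no dose missed, delayed or changed, and an omission can be partly masked.

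Dose intensity is one of the descriptions of how well the weekly regimen was tolerated. The schedule is planned for Part B (up to 20 subjects) and Part C Cohort 2 (up to 40), that is, up to 60 of about 131. The documents do not say how many are expected to stop at the points where the rules misbehave.

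**Working it through.** **Inputs.** Dosing days are "Day 1, Day 8, Day 15, and Day 22 of Cycles 1 and 2, and Day 1 and Day 15 of subsequent cycles" (Protocol Section 3.1.2). Cycles last 28 days. The dose is 1600 mg throughout (dose level 1 in Protocol Table 4), with each dose on its scheduled day unless stated.

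**Formulas (SAP 6.4).** Exposure weeks = (last dose day − 1 + 7 or 14)/7. ADI = total mg/exposure weeks. IDI = 1600 mg/wk for nc ≤ 2, otherwise 1600 × (2nc + 4)/(4nc). RDI = ADI/IDI.

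**The SAP's own figures.** 100 mg every two weeks: 100/2 = 50 mg/wk, as stated. For nc ≤ 2: 1600 × 4nc/(4nc) = 1600 mg/wk, as stated. Doses for nc > 2: 4 × 2 + (nc − 2) × 2 = 2nc + 4, as stated. A subject who completes Cycle 3 has a last dose on day 71, 10 doses, and (70 + 14)/7 = 12 weeks. ADI = 16000/12 = 1333.3 and IDI = 1600 × 10/12 = 1333.3, so RDI is 100%. The table is right for whole cycles.

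**1. Overlap at two cycles (IDI 1600 mg/wk).**

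| Last dose | Day | mg given | RDI with +7 | RDI with +14 |
|---|---|---|---|---|
| C2D1 | 29 | 8000 | 8000/5 = 1600; 100% | 8000/6 = 1333.3; 83.3% |
| C2D8 | 36 | 9600 | 9600/6 = 1600; 100% | 9600/7 = 1371.4; 85.7% |
| C2D15 | 43 | 11200 | 11200/7 = 1600; 100% | 11200/8 = 1400; 87.5% |
| C2D22 | 50 | 12800 | 12800/8 = 1600; 100% | 12800/9 = 1422.2; 88.9% |

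The first three rows count Cycle 2 as received once started.

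**2. Partial last cycle beyond Cycle 2, started cycles counted.**

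| Last dose | Day | mg given | ADI | IDI | RDI |
|---|---|---|---|---|---|
| C3D1 | 57 | 14400 | 14400/10 = 1440 | 1600 × 10/12 = 1333.3 | 108.0% |
| C4D1 | 85 | 17600 | 17600/14 = 1257.1 | 1600 × 12/16 = 1200 | 104.8% |
| C6D1 | 141 | 24000 | 24000/22 = 1090.9 | 1600 × 16/24 = 1066.7 | 102.3% |

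With one dose missed and a stop after C3D1, ADI is 12800/10 = 1280 and RDI is 1280/1333.3 = 96.0%, although 8 of 9 scheduled doses (88.9%) were given.

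**Completed cycles counted instead.** A stop after C3D1 has nc = 2; with +7 days, ADI is 14400/9 = 1600 and RDI is 100%. A stop after C4D1 has nc = 3, and RDI is 1257.1/1333.3 = 94.3%. Neither way of counting gives a compliant subject 100% everywhere.

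**3. Check of the remedy.** Take IDI as planned dose through the planned day of the last dose received, over planned time to that day plus the planned interval.
- Compliant stop after C3D1: IDI = 14400/10 = 1440 = ADI; 100%.
- One missed dose, stop after C3D1: 1280/1440 = 88.9%.
- Eight doses with a 3-day shift, so 59 days instead of 56: ADI = 12800 × 7/59 = 1518.6, IDI = 12800/8 = 1600; 94.9%.

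Dividing planned dose by the actual exposure time would not do: time cancels, and the delayed subject would show 100%.

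**The case against.** The overlap is very probably a slip of wording. The IDI table in the same section splits at more than two cycles, and only the 7-day end date fits weekly dosing in Cycle 2. A programmer who read the two together would choose it, and the 83.3% to 88.9% values would vanish. That stands as to intent. The text as written still allows both, and correcting it leaves the second fault untouched.

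The 108.0% depends on counting a started cycle. If only completed cycles count, the C3D1 stop gives 100%, and the missed-dose example gives 12800/9 = 1422.2, or 88.9% of 1600. This also stands, and it shows that part of the gap is the undefined cycle count. Counting completed cycles then fails at C4D1, with 94.3%.

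RDI is also not the only view of tolerability. SAP Section 6.4 summarises cumulative dose, number of cycles and dose modifications by type and cycle. Section 6.6.1 tabulates adverse events leading to elimination, delay, interruption, reduction and discontinuation. Omitted doses can be seen there, and under started-cycle counting the excess shrinks with longer treatment. This limits the importance of the point but does not make the rule correct.

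A reader might infer that one compliant subject could be assigned any of 83%, 89%, 100% or 108%. The documents do not support that. These values belong to different stopping points; the overlapping bullets give a subject two candidates, and 108.0% has nothing to do with the overlap. Nor does the duration rule assume a complete last cycle: that assumption sits in the IDI formula.

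**Conclusion.** The point holds as two limited defects in SAP 6.4. The duration bullets contradict the section's own IDI split at exactly two cycles, which makes RDI for a compliant 1600 mg subject 100% or 88.9% after C2D22, and 100% or 83.3% after C2D1. The C2D1 figures assume that a started Cycle 2 counts as a cycle. Beyond two cycles, whole-cycle IDI is set against ADI over actual time, with partial cycles undefined. A compliant subject then shows 108.0%, 104.8% or 102.3% on stopping after Day 1 of Cycle 3, 4 or 6 if started cycles count, or about 94% after C4D1 if only completed cycles count.

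All figures assume 1600 mg throughout and dosing on schedule. The standard two-weekly schedule is not affected: its fixed IDI and 14-day end date give 100% at any stopping point.

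It would be wrong to infer that dose decisions are at risk. The run-in rules in Protocol Sections 3.1.2 and 3.1.3.2 use DLT counts, and no DLT, MTD or efficacy analysis uses RDI. The effect is confined to descriptive ADI and RDI, so this is a worthwhile correction of low severity.

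**What to change.** 1. In the second duration bullet, replace the condition by more than two cycles, to match the IDI table. State that the cycle of the last dose received decides the band: 7 days if it is Cycle 1 or 2, 14 days if later. Partial cycles are then settled too.
2. Replace the IDI formula for this schedule by the planned dose scheduled through the planned day of the last dose received, divided by the planned time to that day plus the planned interval (7 days in Cycles 1 and 2, 14 days after). The divisor must be planned time, not actual exposure time, or delays would no longer lower RDI.

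A compliant subject then has 100% wherever treatment stops, while delays and missed doses up to the last dose received still reduce it. Doses omitted after the last one received are not captured; the discontinuation and dose-elimination tables have to show those.

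The cost is a few lines of SAP text and programming, with no new data. If the database is already locked, the SAP introduction allows the change to be documented in the clinical study report.

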3.1.3.2. Part C: Dexamethasone Combination Therapy Cohorts

Enrollment into dexamethasone combination therapy cohorts may be initiated upon identification of tolerable SEA-BCMA monotherapy doses and schedules as determined by the SMC.

- In Cohort 1
 - SEA-BCMA will be administered at 1600 mg (the recommended monotherapy expansion dose) on Day 1 and Day 15 of each 28-day cycle (standard dosing).
 - Dexamethasone will be administered on Day 1, Day 8, Day 15, and Day 22 of each 28-day cycle.
- In Cohort 2
 - SEA-BCMA will be administered
 - at 800 mg (one dose level below the recommended monotherapy expansion dose) on Day 1, Day 8, Day 15, and Day 22 of Cycles 1 and 2 (intensive dosing), AND
 - at 1600 mg (the recommended monotherapy expansion dose) on Day 1 and Day 15 of Cycle 3 and subsequent cycles
 - Dexamethasone will be administered on Day 1, Day 8, Day 15, and Day 22 of each 28-day cycle.

In Cohort 2, a 3-subject cohort will be evaluated at dose level –1 ([Table 4](#)) initially. If 2 or more DLTs occur among the first 3 subjects, then Cohort 2 will be discontinued. If 1 DLT occurs among the first 3 subjects, the cohort will be expanded to 6 subjects, and only escalated if there are fewer than 2 DLTs among the 6 subjects. If 0 DLTs occur among the first 3 subjects, the dose will be escalated to 1600 mg q1wk for 2 cycles and then 1600 mg q2wk from Cycle 3 and beyond, the 6-subject safety run-in rules outlined below will be applied, and 3 additional subjects will be treated at 800 mg to complete the 6-subject safety run-in.

In Cohort 1 and Cohort 2, DLTs will be evaluated in the first 6 subjects enrolled at each dose level tested, in each combination therapy cohort.

1. If 0 or 1 of the first 6 subjects experience DLTs, the expansion cohort will proceed to enroll up to 20 subjects with the recommendation of the SMC.
2. If ≥ 2 DLTs occur in the first 6 subjects, MTD for the combination will be considered exceeded and the dose of SEA-BCMA will be de-escalated to the next lower dose level.
- If 0 or 1 of the first 6 total subjects at the lower dose level have experienced a DLT, the lower dose level will be declared MTD.

- If ≥ 2 DLTs occur in the first 6 total subjects at the lower dose level, MTD for the combination will be considered exceeded and the SMC will determine whether a further de-escalation will be tested, or if the combination cohort will be discontinued.

Subjects who are deemed not evaluable for DLT during dose finding will be replaced.

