In intensive dosing weekly induction Cycles 1 and 2, if a subject has a clinically significant, unresolved AE that prevents dosing on Day 8, 15, or 22, the dose may be delayed for ≤ 3 days. On the third day, if a subject cannot receive the dose, the dose of SEA-BCMA will be eliminated and the corresponding visit will be skipped; dosing and visit schedule would resume the following week (eg, at Day 22, if Day 15 is skipped). However, if a Day 8, 15, or 22 dose is delayed for ≤ 3 days, subsequent study assessments within the same cycle will be delayed by the same number of days as the dose delay, and study drug administration for the next dose will be delayed by at least the same number of days.

During the DLT period (Cycle 1), growth factor and transfusion support is discouraged unless medically indicated; subjects who receive growth factor (eg, granulocyte colony-stimulating factor or granulocyte-macrophage colony-stimulating factor) or transfusion support (other than

red blood cell transfusions for MM-related anemia) during this period for reasons other than DLT may not be evaluable for DLT, except in Part D, where granulocyte colony-stimulating factor is permitted during Cycle 1 if given as primary or secondary prophylaxis in conjunction with pomalidomide. Consideration should be given for growth factor support for prophylaxis or treatment of cytopenias in subsequent cycles (Table 5). During dose-escalation, subjects with Grade 4 neutropenia must have a follow-up complete blood count (CBC) with differential obtained 5 days from the time of assessment for evaluation of DLT. In addition, subjects with Grade 3 asymptomatic laboratory abnormalities must have follow-up laboratory evaluation obtained 72 hours from the time of assessment for evaluation of DLT. Serum chemistry and CBCs should be collected minimally on a weekly schedule during dose delays resulting from toxicity.

Table 5 describes the recommended dose modifications for toxicity.

Table 5: Recommended dose modifications for toxicity

Toxicity	Grade 1	Grade 2	Grade 3	Grade 4
Nonhematologic (AE or laboratory abnormality)	Continue at same dose level	Continue at same dose level	Withhold dose until toxicity is \leq Grade 1 or baseline ^a , and then resume treatment at 50% of the SEA-BCMA dose	Discontinue study treatment

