3 STUDY DESIGN

This is a phase 1, open-label, multicenter, dose-escalation study designed to evaluate the safety, tolerability, and antitumor activity of SEA-BCMA monotherapy and combination in adults with RRMM. The study will be conducted in 4 parts:

Part A: Monotherapy dose-escalation and expansion

Dose-escalation: Up to approximately 25 subjects will be treated with SEA-BCMA monotherapy q2wk to evaluate the safety and tolerability of SEA-BCMA, and to identify the MTD or optimal dose.

Expansion: Up to approximately 20 subjects will be treated with SEA-BCMA monotherapy at dose levels not exceeding the MTD or optimal dose to further characterize the safety and antitumor activity of SEA-BCMA.

Part B: Monotherapy intensive dosing. Up to 20 subjects will be treated at the recommended dose in an expansion cohort testing weekly induction dosing (q1wk) of SEA-BCMA for 8 weeks, followed by q2wk maintenance dosing. This expansion cohort will begin with a 6-subject safety run-in with dose de-escalation permitted.

Part C: Dexamethasone combination therapy cohorts. Up to approximately 60 subjects may be enrolled to evaluate the safety and antitumor activity of SEA-BCMA in combination with dexamethasone.

Cohort 1: The standard dosing combination cohort will combine dexamethasone with SEA-BCMA administered q2wk. This expansion cohort will begin with a 6-subject safety run-in with dose de-escalation permitted. Cohort expansion up to 20 subjects may occur, if permitted after completion of the safety run-in.

Cohort 2: The intensive dosing combination cohort will combine dexamethasone with SEA-BCMA administered q1wk for 8 weeks, followed by q2wk dosing. This expansion cohort will complete a 6-subject safety run-in at 800 mg SEA-BCMA intensive dosing (dose level -1) and, if deemed tolerable, will be followed by a 6-subject run in at 1600 mg SEA-BCMA intensive dosing. Cohort expansion up to a total of 20 subjects may occur in each of up to 2 dose level cohorts, eg, 800 mg and 1600 mg SEA-BCMA dose levels, if permitted after completion of each safety run-in.

Part D: Pomalidomide and dexamethasone combination therapy cohort. Up to 6 DLT evaluable subjects may be enrolled in this safety run-in cohort to evaluate the safety of

SEA-BCMA administered q2wk in combination with pomalidomide and dexamethasone. Part D will be conducted in the US only.

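### SAP 6.4 gives intended dose intensity no maintenance-dose term, so literal use at the 800 mg intensive level shows a fully compliant subject at 120% RDI after 3 cycles and 150% after 6

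*SAP*

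**What the plan says.** SAP 6.4 (Treatment Administration) reports cumulative dose, absolute dose intensity (ADI) and RDI by dose level, with RDI = ADI/IDI. It defines IDI in general as the intended dose in mg per unit of time. For weekly induction over 2 cycles followed by q2wk dosing, its table has rows for one initial dose only, 1600 mg:

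- nc ≤ 2: IDI = 1600 mg/wk
- nc > 2: intended number of doses nd = 2nc + 4, and IDI = 1600 × nd/(4nc) mg/wk

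A footnote covers every other level: "the algorithm is similar for other initial dose level". No maintenance dose appears in the table.

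The protocol gives the other planned intensive level two different doses. In Part C Cohort 2 (Protocol 3.1.3.2) the first two cycles are dosed "at 800 mg (one dose level below the recommended monotherapy expansion dose) on Day 1, Day 8, Day 15, and Day 22"; after induction the plan changes to dosing "at 1600 mg (the recommended monotherapy expansion dose) on Day 1 and Day 15 of Cycle 3 and subsequent cycles". Part B dose level −1 (Protocol 3.1.2 and Table 4) has the same split: "800 mg q1wk x 8 weeks during Cycles 1 and 2, followed by 1600 mg q2wk from Cycle 3 and beyond". SAP Section 3 names the 800 mg intensive level but does not state its maintenance dose.

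On exposure duration, SAP 6.4 adds 7 days to the last dose date for subjects with two cycles or fewer. The next bullet, which adds 14 days, begins "If subjects received 2 and more cycles".

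**The concern.** The SAP formula multiplies every intended dose by the initial dose. That works when induction and maintenance doses are equal, as at 1600 mg. It fails at the only other intensive level the protocol specifies, where the planned dose doubles at Cycle 3. Literal use understates what was intended and so inflates RDI, by more the longer the subject stays on treatment.

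Part C Cohort 2 starts at 800 mg. If both levels are tolerable, 800 mg and 1600 mg may be expanded in parallel by random allocation, up to 20 subjects each. The optimal dose and schedule with dexamethasone is part of a primary objective. The distorted RDI column would therefore sit beside the level a reader would most want to compare it with, and it could make reduced dosing look like full dosing.

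Separately, exactly two cycles satisfies both exposure-duration bullets, while the IDI table splits at ≤ 2 and > 2.

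**Working it through.** **Inputs**

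- Induction: 8 doses (Days 1, 8, 15, 22 of Cycles 1 and 2), Protocol 3.1.2 and 3.1.3.2.
- Maintenance: 2 doses per cycle from Cycle 3, so 2(nc − 2) doses.
- Doses: 1600/1600 mg, or 800/1600 mg at the lower intensive level.
- Exposure duration beyond 2 cycles: last dose date + 14 − first dose date (SAP 6.4). With the last dose on Day 15 of cycle nc, this is 28nc days = 4nc weeks.

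**Step 1: the SAP's own case, 1600/1600 mg**

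Number of doses = 8 + 2(nc − 2) = 2nc + 4, which matches the SAP. At nc = 3, the total is 10 × 1600 = 16,000 mg over 12 weeks. ADI = 1333.3 mg/wk, IDI = 1600 × 10/12 = 1333.3 mg/wk, and RDI = 100%. At nc = 6, the total is 25,600 mg over 24 weeks. ADI = IDI = 1066.7 mg/wk and RDI = 100%. The table is right for the dose it prints.

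**Step 2: the 800/1600 mg level, fully compliant, nc > 2**

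- Total = 8 × 800 + 2(nc − 2) × 1600 = 6400 + 3200nc − 6400 = 3200nc mg.
- ADI = 3200nc/(4nc) = 800 mg/wk.
- Literal SAP IDI = 800 × (2nc + 4)/(4nc) = 400 + 800/nc mg/wk.
- RDI = 800/(400 + 800/nc) = 2nc/(nc + 2).

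| nc | ADI (mg/wk) | Literal IDI (mg/wk) | Literal RDI |
|---|---|---|---|
| ≤ 2 | 800 | 800 | 100% |
| 3 | 800 | 666.7 | 120% |
| 4 | 800 | 600.0 | 133% |
| 6 | 800 | 533.3 | 150% |
| 12 | 800 | 466.7 | 171% |
| 24 | 800 | 433.3 | 185% |

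The limit is 200%. Keeping 1600 mg as the constant does not help: the compliant subject's RDI would be nc/(nc + 2), which is 60% at nc = 3 and 75% at nc = 6.

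**Step 3: can it hide under-dosing?**

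Suppose every maintenance dose is half the planned dose. A 50% step is the size used in Protocol Table 5, where a subject may "resume treatment at 50% of the SEA-BCMA dose".

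- 800 mg level: received 800 × (2nc + 4) mg, so literal RDI = 100% at any nc. Against plan, 800(2nc + 4)/(3200nc) = (nc + 2)/(2nc).
- 1600 mg level: [12,800 + 1600(nc − 2)]/[1600(2nc + 4)] = (nc + 6)/(2nc + 4).

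| nc | 800 level, literal | 800 level, against plan | 1600 level |
|---|---|---|---|
| 3 | 100% | 83% | 90% |
| 6 | 100% | 67% | 75% |
| 12 | 100% | 58% | 64% |

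**Step 4: exactly two cycles**

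The last dose of a compliant subject falls on Day 28 + 22 = 50. Adding 7 days gives 50 + 7 − 1 = 56 days = 8 weeks and RDI 100%. Adding 14 days gives 63 days = 9 weeks and RDI 8/9 = 88.9%. This applies at both intensive levels.

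**The case against.** The best defence is that the SAP's general definition governs. IDI is the intended dose per unit of time, the table works one example, and the footnote says similar, not identical. The SAP's label for the 800 mg intensive level, dose level −1, also matches the Protocol Table 4 row that states both doses. A careful programmer could follow that trail, reach 800 mg/wk and report 100%. This is fair, and the final programs may already be right. But the table is indexed by initial dose alone, the adapted formula is nowhere written, and the only other planned intensive level is the one where the pattern breaks. The protocol leaves the details of dose intensity to the SAP, so the rule belongs there.

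The longer durations may be rare. The one late-line benchmark in Protocol 1.1, for another regimen, is a median PFS of 3.7 months, or about 4 cycles (3.7 × 30.4375/28 = 4.0). At 4 cycles the literal RDI is already 133%. Halving every maintenance dose is a constructed illustration.

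RDI at 1600 mg is not a perfect comparator either. A compliant subject whose last dose is Cycle 3 Day 1 has 9 × 1600 mg over 10 weeks = 1440 mg/wk against an IDI of 1333.3, so RDI is 108%. This stands, but it is an existing feature of counting whole cycles. It is separate from the missing maintenance-dose term.

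The two-cycle overlap is a wording slip whose intent can be read from the neighbouring IDI table. It still yields two different answers for the same subject.

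**Conclusion.** The concern holds. As written, SAP 6.4 does not define a correct IDI for the 800 mg intensive level beyond Cycle 2. Literal use gives a fully compliant subject an RDI of 2nc/(nc + 2). The SAP's printed 1600 mg figures are correct.

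The consequence is limited. RDI is descriptive, is not among the listed endpoints and enters no dosing or analysis decision. Cumulative dose, ADI, the dose-modification tables and the adverse event tables would still show reductions. Only subjects at the 800 mg intensive level treated beyond Cycle 2 are affected by the IDI gap. Their number is not known from the documents; the ceiling is 20 in Part C Cohort 2, plus Part B subjects only if that part was de-escalated.

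The figures assume that 800 mg replaces 1600 mg throughout the SAP formula, that all doses are given on schedule, and that ADI uses the exposure duration defined in SAP 6.4. The protocol's planned doses are taken as given.

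**What to change.** In SAP 6.4, define IDI from the protocol-planned dose in each phase. For nc > 2:

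IDI = [8 × induction dose + 2(nc − 2) × maintenance dose]/(4nc) mg/wk

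Print the 800/1600 mg row next to the 1600 mg row. For 800/1600 mg the formula gives 3200nc/(4nc) = 800 mg/wk and RDI 100% for the compliant subject at any nc > 2. For 1600/1600 mg it reduces to the SAP's present expression, so those rows do not change.

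Reword the second exposure-duration bullet to apply to more than 2 cycles, in line with the IDI table.

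The cost is a short SAP edit and a small programming change or check. No new data are needed and no planned dose is altered. If the SAP is no longer open to amendment, state the IDI rule actually used in the clinical study report.
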